(e.g. if baseline trials indicated a pressure threshold of 50 N then subject will be asked to evaluate the pain of that stimulus). During final testing trial (day 29), the pressure pain threshold will be re-measured to determine if there is a change from baseline. For the quality/unpleasantness testing, subjects will be tested on day 29 at their original baseline pressure threshold (from day 1) AND the new threshold determined day 29. This will allow an analysis of change from baseline and pain at threshold across the experiment.

Following baseline pain testing, subjects (in the exercise only and meditation then exercise groups) will be set-up for training on the exercise protocol. Subjects will become familiarized with the exercise protocol, including the physiological measures to be assessed [heart rate (HR)], the Borg Rate of Perceived Exertion (RPE) Scale, and the treadmill speed at which they will be walking. Subjects will be instructed to step up onto the treadmill and stand on the sides not the belt or belt deck. The researcher will slowly raise the speed to 2 mph. The subject will be instructed to step on the treadmill at this time. After 30 seconds, the speed will be ramped up to 2.5 mph and after another 30 seconds, the speed will be ramped up to their prescribed session speed (± 3.5 mph). They will also be instructed to walk with a natural gait pattern, allowing bilateral arm swing. To allow a natural arm swing, subjects are unable to hold onto the treadmill arm rails. Subjects will be introduced to the Borg RPE scale and asked to provide subjective feedback on their level of exertion at the initiation of and during the final minute of this 5 minute training period (Borg).

Intervention Sessions

Subjects will be scheduled for 20 intervention sessions during their time in the study – that is five sessions per week over four weeks. Subjects are only required to return to campus for the first session of each week. The remaining four weekly sessions can be completed at home on a personal treadmill or in the community, such as a local gym. Subjects are able to complete all sessions at Duquesne University if that is their preference. Sessions will be scheduled/encouraged to occur at the same approximate time each day to control for factors that may influence exercise performance and assessments.

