Compensation for participation in this study is based on the number of sessions completed. Compensation for the intake session and each completed intervention session is \$4.50 and compensation for the Exit Session is \$100. Therefore, if a participant completes this project in its entirety (intake session, 20 intervention sessions, and the Exit session), they will receive \$200. Only participants who complete at least 80% of all intervention sessions (greater than 16 of 20 sessions) and the intake session, will be invited to complete the Exit Session. If the subject chooses to withdraw before completing at least 80% of the intervention sessions, they will receive partial compensation for the sessions that they have completed.

As part of this study, we are also interested in identifying barriers to participant interest and persistent. To identify these barriers, we will utilize an anonymous online survey of participants who drop out of the study. If a participant consents to the Duquesne study but later drops out of the study, they will be directly given a URL for a survey.

7. Informed consent procedures for exercise/meditation study

As noted above, initial consent is obtained through the University of Pittsburgh Department of Physical Meditation and Rehabilitation Research Registry (PMR3) (Pitt IRB # PRO12030122). This consent is obtained by UPMC/Pitt Physician [name] (co-I), and his partners, Drs. [name], [name], and [name] (see *Support Letter*) along with Physical Medicine and Rehabilitation Clinical Research Coordinator [name], MS. Backup recruitment efforts will occur in collaboration with the CTSI (see *Support Letter*) using the Pitt + Me registry. IRB approved consent is provided when patients are entered into the Pitt + Me registry.

Subsequent consent for the exercise/meditation study here at Duquesne occurs as follows:

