Subjects will be notified of their rights, all risks and benefits of participation in this study during the informed consent procedure. Subjects will be informed that they may withdraw from participation at any time. Data collection sessions will be scheduled at times that are mutually convenient for the subject and the researchers and all efforts will be made to work with the subject's schedule.

Subjects will be instructed that they are able to stop intervention and pain measurements at any time if they experience excessive discomfort/pain. Treadmill exercise occurring at Duquesne will be monitored visually by a researcher in the adjacent room using a wireless camera system. Physiological measures, including heart rate, will also be monitored in real-time to ensure no issues during exercise. Subjects will be encouraged to stop exercise if they experience any discomfort or symptoms of over-exertion (≥ 17 on the Borg RPE scale). These symptoms will be explained during the informed consent process. There is a risk of falling off the treadmill. Subjects will be instructed to hold onto the rails if they feel like they are losing their balance or are going to fall.

The safety key will be on the waist of their pants to turn off the treadmill if they move too far back on the belt. Specific instructions will be given to patients who exercise or participate “at home.”

Though the likelihood is minimal, there is also a risk of a serious cardiac event, including loss of consciousness, chest pain, shortness of breath, and myocardial infarction, associated with performing moderate intensity exercise. To minimize this risk, eligibility criteria have been set to ensure healthy adults with low risk are enrolled in this study.

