During exercise at Duquesne, participants will be monitored for signs associated with a cardiac event based on the American College of Sports Medicine (ACSM) *Indications for Terminating Exercise Testing* protocol. These indications include: onset of angina, signs of poor perfusion (dizziness, confusion, light-headedness, ataxia), failure of heart rate to rise with exercise, severe fatigue, or subject request to stop. To determine if any of these indications occur, participants will be visually monitored and heart rate will be displayed in real-time at Duquesne trials. All participants will be notified that they may stop exercising if they feel short of breath, chest pain, abnormal back pain, or extremely fatigued. Also, patients are instructed that if they feel that their exertion reaches a 17 on the Borg Scale, they can stop walking. All research staff will be trained on this protocol and medical emergency management associated with a medical event. An emergency action plan will be stored in the laboratory and will be reviewed quarterly. [name], MD will serve as our medical PI on this study. Any adverse reaction will be evaluated by [name] within 1 week of the event. “At home” trials will be additionally monitored through an online diary using Qualtrics Survey Platform, which allows the patient to record adverse events for the PIs. Qualtrics is supported by both Duquesne University and the University of Pittsburgh for research using surveys. Qualtrics servers are protected by high-end firewall systems and use Transport Layer Security encryption for all transmitted data. For ‘at home’ trials, subjects cannot be monitored for signs associated with a cardiac event, however, subjects will be made fully aware of these signs and told to stop exercising if they experience any of these symptoms. Subjects will be instructed to contact [name] or [name] via a Google Voice number immediately when these symptoms occur. If these symptoms do not resolve within 15 minutes of resting, subjects will be instructed to seek medical help. Any adverse events will be discussed immediately (subjects will have [name], [name] and [name] contact information) and during the single trial that occurs each week at Duquesne. To ensure [name] or [name] is available to take these phone calls, a Google Voice number will be set up. This is the phone number subjects will be given. Calling this number will route the call to any of [name] or [name] existing phone numbers while maintaining privacy of personal contact information.

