
Risk of injury related to cutaneous mechanical testing is extremely rare and unlikely⁴. Mechanical testing is widely used and safe. Risks to the individual are minimal, because 1) subjects are instructed that they may stop any procedure at any time with no adverse consequences; and 2) the level of sensation experienced by subjects is at or below their tolerance level and threshold for pain.

Risk of injury related to thermal pain testing is minimal⁴. Thermal testing is widely used and safe. While thermal testing does produce pain, risks to the individual are minimal, because 1) the pain is transient in nature and generally subsides immediately after the procedure; 2) subjects are instructed that they may stop any procedure at any time with no adverse consequences; and 3) the level of pain experienced by subjects is below their tolerance level. With thermal stimulation there is a very slight risk of a burn, but this is minimized by the following: 1) positive lockout of stimulus parameters above 50°C; 2) the stimulator has built in a shut-down system to prevent the delivery of prolonged or high intensity stimuli (20 sec); 3) and before each use, temperature at probe will be verified with an electronic thermometer. Trials will proceed only if temperature detected at 20 sec cutoff is $\leq 50^{\circ}\text{C}$. Colleagues who have used this pain paradigm inform us that they have completed thermal testing with this stimulator on over 1000 subjects without producing a single burn. However, skin will be monitored for changes consistent with burns, such as redness that persists greater than one day and blistering. If a burn occurs, standard medical treatment will be recommended.

Risk of injury related to pressure pain testing is minimal^{4,7}. Pressure testing is widely used and safe. While pressure testing does produce pain, risks to the individual are minimal, because 1) the pain is transient in nature and generally subsides immediately after the procedure; 2) subjects are instructed that they may stop any procedure at any time with no adverse consequences; 3) the level of pain experienced by subjects is below their tolerance level; and 4) the pain applied is never more than that subjects pain threshold, which is well below any pressure that could cause damage.

Participants will be made aware during the consent process that they may withdraw from participation at any time during their enrollment.

URLS TO GUIDED MEDITATION RECORDINGS

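### The 80% attendance rule for the day-29 visit is stated as both 16 and 17 of 20 sessions, and it removes low-adherence randomised participants from the end-of-study QST, FABQ and exit survey

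*Protocol*

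**What the plan says.** Protocol section 6 sets the condition for the Exit Session: "Only participants who complete at least 80% of all intervention sessions (greater than 16 of 20 sessions", together with the intake session. The next sentence, on partial pay, uses the percentage alone: "If the subject chooses to withdraw before completing at least 80% of the intervention sessions". Intake and each completed intervention session pay $4.50, the Exit Session pays $100, and the stated total is $200. The Protocol does not say what makes a session completed, and it describes no make-up session.

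Section 3 counts 22 sessions in all: 20 intervention, one intake and one outtake. Its Figure 1 places the pain assessment and exit survey in clinic on day 29. Section 4 schedules the QST at baseline and day 29, the FABQ on days 1 and 29, and the exit survey on day 29. The SAP compares groups on change in 14 QST measures and on change in the FABQ.

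On symptoms, section 9 says "Subjects will be encouraged to stop exercise if they experience any discomfort or symptoms of over-exertion", and participants are told "they may stop exercising if they feel short of breath, chest pain, abnormal back pain, or extremely fatigued". Neither statement is linked to session credit or to the Exit Session.

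**The concern.** Three things follow from the rule as written.

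First, a participant with exactly 16 completed sessions qualifies by the percentage and fails by the count in brackets.

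Second, and most important, a payment rule decides who is measured at the end of the study. A participant who is randomised, has not withdrawn and would be willing to attend is still not invited if adherence was low. Adherence arises after randomisation and may depend on how well the assigned regimen was tolerated. The remaining day-29 sample is therefore selected on tolerance. Section 2 says that feasibility will be judged by recruitment, retention and treatment acceptance, and the exit survey asks about the likelihood of continuing to meditate or exercise. Under this rule, only people who largely kept to the regimen answer it.

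Third, and secondary, the rule makes no allowance for sessions missed because of symptoms. Much of the exercise can be done away from the site ("Subjects are only required to return to campus for the first session of each week"), where "subjects cannot be monitored for signs associated with a cardiac event". A large payment tied to session count gives some reason to carry on.

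**Working it through.** **Inputs.** 20 sessions, five per week for four weeks (section 3). Payment rates and both cut-off wordings (section 6). Timing of assessments (sections 3 and 4). Comparisons (SAP, paragraph on secondary responses).

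**1. The cut-off.** 0.80 × 20 = 16, so at least 80% means 16 or more. More than 16 means 17 or more, and 17/20 = 85%. The bracketed count does not reproduce the percentage.

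**2. Who is invited, and the pay.** Pay for n completed sessions is 4.50 × (n + 1), plus 100 if the Exit Session is attended.

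| Missed | Done | Share | At least 80% | More than 16 | Pay |
|---|---|---|---|---|---|
| 0 | 20 | 100% | invited | invited | $194.50 |
| 3 | 17 | 85% | invited | invited | $181.00 |
| 4 | 16 | 80% | invited | not invited | $176.50 or $76.50 |
| 5 | 15 | 75% | not invited | not invited | $72.00 |

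Up to three misses for any reason are tolerated under both wordings, four is ambiguous, and five fails both. One full week missed (5 sessions) gives 20 − 5 = 15.

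**3. Which visit is lost.** 22 − 20 − 1 = 1, so there is a single outtake visit, and Figure 1 places it on day 29. The Exit Session is therefore the day-29 visit.

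**4. Which data are lost for an uninvited participant.**
- QST: measured only at baseline and day 29, so no change score can be formed.
- FABQ: measured only on days 1 and 29, so the same applies.
- Exit survey: day 29 only, so lost.
- RMDQ (primary): neither document gives a post-treatment day, so loss is possible but not established.
- Daily back-pain VAS and state anxiety around each session: retained for sessions done.
- FMI: section 3 puts the second administration on day 27, section 4 on the last day of the trial, so loss is unclear.

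The SAP names no analysis population and no method for missing values. A two-sample test on change will simply omit these participants.

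**5. The payment.** The exit payment is 100/194.50 = 51% of full pay. Crossing the cut-off changes the attainable total by 181.00 − 76.50 = $104.50 under one wording, or 176.50 − 72.00 = $104.50 under the other. Of that, $4.50 is for the session and $100 is for attending a further visit. Off-campus sessions can number 4 × 4 = 16 of the 20.

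**6. The stated total.** 21 × 4.50 + 100 = $194.50, not $200. Counting the exit visit at $4.50 as well gives 22 × 4.50 + 100 = $199.00, which does not match either.

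**The case against.** The strongest reply is that the documented defect is a slip of one in a bracket. The percentage appears twice and points to 16, so only participants with exactly 16 sessions are affected. That is fair for the conflict itself. It does not touch the exclusion at 15 or fewer, which holds under both wordings.

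A second reply is that the data loss is limited: daily measures survive, section 8 reports adherence and withdrawal proportions whatever the exit rule, and dropouts are sent a survey. This also stands in part. However, the survey goes to those who drop out rather than to low adherers who stay, and because it is anonymous it cannot be joined to a participant's baseline.

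A reader might infer something stronger: that the plan penalises participants for obeying safety instructions, or pays them to exercise through symptoms. The documents do not support that.
- They tell participants to stop within a session. They order no pause afterwards, and section 3 lets walking speed be lowered.
- Because completion is undefined, a session stopped early may count. Three misses are free in any case.
- Participants at home also have an online diary, a number to call, medical evaluation within a week, and discussion "during the single trial that occurs each week at Duquesne".
- Supposing a pause after a symptom, the number of the 20 possible event days that would fail both wordings runs from 0 (pauses of up to 3 days) to 16 (6 or 7 days, event session not counted). These are counts of days with no event rate attached, and the range is too wide to size the problem.
- The assurance that "subjects are instructed that they may stop any procedure at any time with no adverse consequences" is given for the sensory and pain tests, so the exit rule does not contradict it.

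What remains is that no exception exists in the text and the payment points one way. The treadmill stop instructions concern only the two exercise arms. The consent form and the home instructions, which might address credit, are not in the documents.

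**Conclusion.** The point holds as a design weakness that should be corrected. The cut-off contradicts itself at exactly 16 sessions. At 15 or fewer, a randomised participant is barred from the visit that supplies the end-of-study QST, FABQ and exit survey, so those results rest on a sample selected by post-randomisation adherence.

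The size cannot be given, because the documents state no expected adherence and no symptom rate. Two further inferences are tempting but not established. One is that the primary outcome is lost, which depends on an RMDQ day that is not stated. The other is that the loss biases the comparison in a known direction, which depends in part on which control group the SAP means, and the SAP does not say. The incentive to continue through symptoms is secondary: real in direction, unknown in size. The payment total is a separate clerical error of 200 − 194.50 = $5.50.

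The conclusion assumes that the invitation rule is applied as written and that no other document provides an end-of-study visit for those below the cut-off.

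**What to change.** Amend Protocol section 6, and the consent form to match:

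1. Invite every randomised participant who has not withdrawn to the day-29 assessments, and pay the $100 for attending.
2. Keep one threshold, 16 of 20 (at least 80%), as an adherence measure only, and say what counts as a completed session.
3. Correct the total to $194.50, or adjust the rates.

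The first change closes the data gap and removes the payment incentive together. It is preferable to crediting symptom-related misses as completed, which would pay $100 on self-reports that cannot be verified, could encourage symptom reporting, and would leave other low adherers unmeasured.

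The cost is wording, plus $100 and one visit for each otherwise uninvited participant who attends. The financial incentive for adherence becomes weaker, with $4.50 per session remaining. Honouring $200 would cost $5.50 per completer.

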Title Page:

Statistical Analysis Plan

Combined exercise and meditation as a treatment for patients with chronic back pain

NCT number not available

12/21/17

Statistical Analysis Plan
Combined exercise and meditation as a treatment for patients with chronic back pain

This is a single-blind, single center randomized clinical trial comparing a treatment group (MedExT) versus a control group. The current analysis plan is specific to this study for reporting and publication purposes but is part of a larger study. The primary outcome of this study is to compare the post Roland-Morris Disability Questionnaire scores between the two independent groups. This will be achieved by comparing the mean post disability score for the MedExT group to the mean post disability score for the control group using a two-sample t-test (or the Mann-Whitney-Wilcoxon rank sum test if normality does not hold) in which a one-sided p-value < 0.05 will be considered a significant improvement in the MedExT group.

Three secondary treatment responses will be studied. The first will test whether the MedExT group will significantly increase mean scores on the Freiburg Mindfulness Inventory as determined by a two-sample t-test or the Rank Sum test given distributional properties of the data ($P < 0.05$). The second will explore whether the MedExT treatment will significantly influence a mean change in responses on the three psychological inventories administered; the Fear Avoidance Beliefs Questionnaire, the STAI state anxiety inventory and the STAI state trait inventory, $p < 0.02$. The third outcome measured will study mean response changes in the series of 14 Quantitative Sensory Tests measured at baseline and at the completion of the 4-week intervention period. Significant mean pre/post differences between groups will be identified using the two-sample t-test or the Rank Sum test where appropriate adjusting the significance level to 0.005. Additionally two pain outcome measures will be repeatedly observed throughout the study taken at baseline and on each intervention day. These measures are the VAS pain intensity score and the VAS pain unpleasantness. A repeated measures multivariate analysis of variance (MANOVA) procedure will be used to determine if the vector of timed responses is significantly different between the two study groups.

The following demographic variables will be collected and compared between groups to further check against potential bias; age, sex, handedness, body mass index (BMI), baseline heart rate (HR), baseline blood pressure (BP), baseline IPAQ-short and mean number of steps taken per day over the 4-week intervention period. Difference in the proportion of sex/handedness will be tested using the Fisher's Exact test where a p-value less than 0.05 will be considered significant. All other continuous variables will be tested using the two-sample t-test to test for significance differences between the two study groups ($p < 0.05$).

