3. Research design and procedures

This study is designed as a randomized single-blinded (for QST testing) trial with repeated measures.

The participants will primarily be recruited through a University of Pittsburgh approved IRB patient registry (Pitt IRB protocol #REN16070141/PRO12030122 "Department of Physical Medicine and Rehabilitation Research Registry (PMR3) see "participant" recruitment below for additional details). Registry use is managed with co-PI [name] (MD, University of Pittsburgh Department of Physical Medicine and Rehabilitation). Secondly, we will recruit from the Clinical and Translational Science Institute's Pitt + Me registry.

The co-primary investigators (co-PIs) will be involved in the procedures listed below. Graduate research students (e.g. [name], Biological Sciences) and technicians will assist with recruitment, data collection, and data processing. These additional technicians have yet to be identified but will be added to the protocol with subsequent amendments. The graduate student and technicians will be trained on all procedures involved in this study by the co-PIs. Prior to data collection, the prospective subjects will complete a full screening, using a checklist of the inclusion/exclusion criteria and the AHA health questionnaire (see “Instruments”) to determine eligibility. The purpose of the study, the methods of data collection and all potential risks will be verbally communicated to prospective subjects at the initiation of the first data collection session (Day 1) (**Figure 1**). Prospective subjects will be given an approved informed consent form to read and sign. Subjects will then complete additional questionnaires to assess baseline activity level and state anxiety (see “Instruments” below). The researcher will explain the questionnaires to subjects and will be available to answer any questions

Figure 1 – Time-line of four week trial for participants in combined intervention group.

Day	1	2	3	4	5	6	7	8	
Activity	-Consent -Intake surveys -Baseline pain assess (In clinic)	-15 min meditation -30 min exercise (In clinic)	-15 min meditation -30 min exercise	Rest	Rest				
Day		9	10	11	12	13	14	15	
Activity		-15 min meditation -30 min exercise (In clinic)	-15 min meditation -30 min exercise	-15 min meditation -30 min exercise	-15 min meditation -30 min exercise	15 min meditation -30 min exercise	Rest	Rest	
Day		16	17	18	19	20	21	22	

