Assessments in this exploratory trial are designed to evaluate four elements of the trial: (1) Pain and Disability, (2) Meditation, (3) Anxiety and Stress, and (4) Fitness and General Health and. Although these elements are not mutually exclusive and multiple survey tools overlap, we describe these elements as individual groups of assessments below for ease of interpretation. General assessment includes demographic information (gender, age, race/ethnicity, and education level) and handedness. The primary outcome of this trial is a reduction in disability as measured by the RMDQ (see below). See Appendix 1 – Instruments for all surveys and questionnaires.

Protocol Pain and Disability

There are multiple assessments for experimental measurement of pain. First, we will use the Roland-Morris Disability Questionnaire, which provide a qualitative analysis of the disability that is associated with an individual's chronic low back pain. This is our primary outcome for the trial. We hypothesize that exercise, meditation, and combined exercise/meditation will decrease disability in patients. Second, we will use standard visual analog scoring of instantaneous back pain for participants before and after exercise (or meditation in the "meditation only" control group or audio book in the negative control group) during each day of the trial. These scales will be included in the subject online diary (Qualtrics Survey Platform) for participants completing "at home" trials.

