At the initiation of the intake day, [name] will explain the purpose of the study, the methods of data collection and all potential risks associated with participation to prospective participants. Prospective participants will then be given an approved informed consent form to read, following the guidelines determined by the Duquesne University IRB. If they agree to participate, they will be asked to sign two copies of the form; one copy to be retained by the PI and the second copy for the subject's records. Hard copies retained by the PI will be stored in a locked cabinet in a locked room. Participants will be made aware during the consent process that they may withdraw from participation at any time during their enrollment.

8. Collection of data and method of data analysis

Qualitative analysis of the online questionnaire will identify main reasons why patients may withdraw from the study. Percentages of eligible participants who withdraw will be carefully monitored and reported providing more accurate estimates of recruitment rates and target population numbers. Proportion estimates will be reported to assess percentages who actually complete the intake questionnaires as well as adherence to the four-week intervention and all daily measurements.

To address the evaluation of the four key elements; meditation, anxiety and stress, fitness and general health, and pain, a variety of analyses and descriptive statistics are necessary to calculate key estimates needed to inform the design and power of a large-scale trial given the different variable types and repeated measures embedded in the methodology. The primary assessment for this study will be a reduction in disability. Means and standard deviations will be reported for all quantitative measures for all groups, effect sizes for comparisons of means and repeated measures, and proportion estimates will be reported for qualitative variables. Where appropriate, correlations between various assessments of mindfulness, pain and disability (self-reported and quantitative measures), anxiety/fear, and activity (i.e. IPAQ-short and exercise performance) will be analyzed.

9. Emphasize issues relating to interactions with subjects and subjects' rights

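### The primary RMDQ test uses no baseline value; if RMDQ is collected on Day 1, adjusting for it would probably improve precision at little cost

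*SAP*

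**What the plan says.** The SAP (primary outcome) specifies one test: "comparing the mean post disability score for the MedExT group to the mean post disability score for the control group using a two-sample t-test". The result is judged at one-sided 0.05. The only alternative it allows is given in brackets: "or the Mann-Whitney-Wilcoxon rank sum test if normality does not hold". It gives no baseline covariate, change score or adjusted sensitivity analysis for RMDQ, and no criterion for deciding that normality fails.

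The protocol describes the endpoint as an improvement. Section 4 (Instruments) says "The primary outcome of this trial is a reduction in disability as measured by the RMDQ", and section 8 (Collection of data and method of data analysis) says "The primary assessment for this study will be a reduction in disability".

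Elsewhere the SAP does use baseline values. It asks whether treatment "will significantly influence a mean change in responses on the three psychological inventories administered", and for quantitative sensory testing it says "Significant mean pre/post differences between groups will be identified using the two-sample t-test".

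On timing, Figure 1 in protocol section 3 lists "Intake surveys -Baseline pain assess (In clinic" on Day 1 and a pain assessment with an exit survey on Day 29. It names RMDQ at neither visit. Section 4 schedules the fear-avoidance questionnaire for Day 1 and Day 29 but has no such sentence for RMDQ. The instruments are in Appendix 1, which is not in the text available for this review, so the timing may be given there.

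Section 8 gives as a purpose of the analyses to "calculate key estimates needed to inform the design and power of a large-scale trial".

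**The concern.** A patient's disability score before treatment usually says something about the score on the same questionnaire four weeks later. A post-only comparison leaves that between-patient variation in the error term. If Day 1 RMDQ exists, the confidence interval is then wider and the power lower than the same data allow, unless the correlation is low.

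This matters for two reasons. First, the primary endpoint would be analysed with less information than the secondary inventories and sensory tests, which use change. Second, the estimates are meant to help plan a larger trial. For that, the baseline-adjusted difference, the residual SD and the baseline-to-post correlation are useful, and the post-only test produces none of them.

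**Working it through.** **Nothing to reproduce.** Neither document gives a sample size, power, SD, effect size or correlation for RMDQ. Only the test and the one-sided 0.05 come from the documents.

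**Assumed inputs.** Equal allocation; 10, 20 or 30 per arm (N = 20, 40, 60); baseline-to-post correlation ρ of 0, 0.3, 0.5 and 0.7; normal scores; complete follow-up.

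**1. Variance.** The ratio of the ANCOVA variance to the post-only variance is

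(1 − ρ²) × (1 + 1/(N − 4)).

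The second factor is the price of estimating the slope. At N = 40 it is 1 + 1/36 = 1.0278, so:

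- ρ = 0.3: 0.91 × 1.0278 = 0.935, a cut of 6.5%
- ρ = 0.5: 0.75 × 1.0278 = 0.771, a cut of 22.9%
- ρ = 0.7: 0.51 × 1.0278 = 0.524, a cut of 47.6%

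| Per arm | ρ = 0.3 | ρ = 0.5 | ρ = 0.7 |
|---|---|---|---|
| 10 | 3.3% | 20.3% | 45.8% |
| 20 | 6.5% | 22.9% | 47.6% |
| 30 | 7.4% | 23.7% | 48.1% |

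**2. Break-even.** Setting the ratio to 1 gives ρ² = 1/(N − 3), so ρ = √(1/17) = 0.24, √(1/37) = 0.16 and √(1/57) = 0.13 at 10, 20 and 30 per arm. Below these values ANCOVA is slightly worse.

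**3. Interval width at 20 per arm.** This is the square root of the variance ratio times the ratio of t quantiles (37 against 38 degrees of freedom): 0.968, 0.879 and 0.725. The 95% interval is about 3%, 12% and 27% narrower.

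**4. Power.** Power needs a starting point, and this is also an assumption. The effect was set so that the post-only test has 60% power (0.611 SD at 20 per arm, 0.882 SD at 10). Power comes from the noncentral t distribution, one-sided 0.05, with ANCOVA averaged over chance baseline imbalance. The change score has variance ratio 2(1 − ρ) if the SDs are equal at both visits.

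| 20 per arm | ρ = 0 | ρ = 0.3 | ρ = 0.5 | ρ = 0.7 |
|---|---|---|---|---|
| Post-only | 60% | 60% | 60% | 60% |
| ANCOVA | 59.0% | 62.5% | 69.7% | 83.5% |
| Unadjusted change | – | 48.4% | 60.0% | 79.0% |

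To match ANCOVA at ρ = 0.3, 0.5 and 0.7, the post-only test would need about 22, 26 and 38 per arm. At 10 per arm and ρ = 0, ANCOVA has 57.8%, a loss of 2.2 points.

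**5. Type I error.** In simulation with normal scores at 10 to 30 per arm, both tests stayed between 4.6% and 5.3%.

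**The case against.** The strongest reply is that a post-score t-test is a legitimate pre-specified analysis of a randomised trial, and that this trial is exploratory with a central hypothesis about feasibility. That stands, and it limits the point to efficiency.

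The size of the gain also rests wholly on assumption. At ρ = 0.3 it is 2.5 power points and a 3% narrower interval, and nothing in the documents supports 0.7. The power gain moves with the assumed starting power: at ρ = 0.7 it is about 21 points from 40%, 16 from 80% and 9 from 90%. This stands too, but the loss at zero correlation is only 1 to 2 points, so the trade still favours adjustment.

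A third reply is that protocol section 8 already promises means, SDs and effect sizes, including for repeated measures. A reader might infer that the larger trial would go without planning inputs; that would be too strong. What is not expressly promised is the baseline-to-post RMDQ correlation and the residual SD.

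Two other readings go too far:

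- A reader might infer that comparing post scores contradicts a primary outcome worded as a reduction. Under randomisation with complete follow-up, post scores and change scores have the same expected difference between arms, so the wording needs clarifying but the target is not wrong.
- A reader might infer that Day 1 RMDQ is not collected. The documents do not show that either; they imply collection without stating it.

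Finally, the complete-follow-up premise is not secure. Protocol section 6 invites only participants with at least 80% of intervention sessions to the Exit Session. If the post RMDQ is taken there, the comparison may rest on a selected group. Baseline adjustment does not remove that selection.

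**Conclusion.** The point holds as a conditional improvement in efficiency. The documents do not support calling the primary test biased or invalid.

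The condition is that RMDQ is collected on Day 1. If it is, adjustment gains precision once the correlation passes about 0.13 to 0.24 at 30 to 10 per arm. At 20 per arm the gain runs from small (6.5% of variance at ρ = 0.3) to large (47.6% at ρ = 0.7), and the documents cannot say where in that range this trial lies. The change is worth making because the possible loss is small and the fix is cheap.

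**What to change.** 1. Confirm, and state in the protocol, that RMDQ is collected on Day 1 and Day 29. If Day 1 is missing, add it at intake. If it cannot be added, keep the post-only test and reword the primary outcome in the protocol to match.
2. Replace the SAP's primary test with: *ANCOVA of Day 29 RMDQ on randomised group with baseline RMDQ as covariate, one-sided alpha 0.05; the adjusted difference is reported with its confidence interval.*
3. Replace the rank sum fallback with rank ANCOVA as a pre-specified sensitivity analysis, not triggered by a normality test. A switch would take the p-value and the interval from different models. In simulation at 20 per arm, a Shapiro-Wilk switch to rank ANCOVA had type I error up to about 5.5%.
4. Do not use an unadjusted change score. In the table above it has less power than ANCOVA at each correlation, and less than the post-only test when ρ is under 0.5.
5. Add the baseline-to-post RMDQ correlation and the residual SD to the estimates promised in protocol section 8.
6. Use the same description of the primary outcome in both documents: RMDQ at Day 29, compared between groups with adjustment for baseline RMDQ.

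The cost is SAP wording, short protocol clarifications and one degree of freedom. If Day 1 RMDQ is not already collected, it also costs one intake questionnaire.
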